2.1.2 Adverse Events

Most frequently reported adverse events reported during clinical studies with lenalidomide in oncologic and non-oncologic indications, regardless of presumed relationship to study medication include: anemia, neutropenia, thrombocytopenia and pancytopenia, abdominal pain, nausea, vomiting and diarrhea, dehydration, rash, itching, infections, sepsis, pneumonia, urinary tract infection, upper respiratory infection, atrial fibrillation, congestive

heart failure, myocardial infarction, chest pain, weakness, hypotension, hypercalcemia, hyperglycemia, back pain, bone pain, generalized pain, dizziness, mental status changes, syncope, renal failure, dyspnea, pleural effusion, pulmonary embolism, deep vein thrombosis, cerebrovascular accident, convulsions, dizziness, spinal cord compression, syncope, disease progression, death not specified and fractures.

2.1.3 Second New Cancers

[figure not shown]
According to researchers, patients with cancer have a higher risk of developing a second new cancer when compared to people without cancer. In clinical studies of patients with newly diagnosed multiple myeloma, a higher number of second cancers were reported in patients treated with lenalidomide as induction therapy (treatment for several cycles to reduce number of cancer cells) and/or bone marrow transplant followed by lenalidomide for a long period of time compared to patients treated with induction therapy and/or bone marrow transplant then placebo (a capsule containing no lenalidomide). Patients should make their doctors aware of their medical history and any concerns they may have regarding their own increased risk of other cancers.

Complete and updated adverse events are available in the Investigational Drug Brochure and the IND Safety Letters.

2.1.4 Lenalidomide Description

REVLIMID® (lenalidomide), a thalidomide analogue, is an immunomodulatory agent with anti-angiogenic properties. The chemical name is 3-(4-amino-1-oxo 1,3-dihydro -2*H*-isoindol-2-yl) piperidine-2,6-dione and it has the following chemical structure:

Figure 3. Chemical Structure of Lenalidomide

3-(4-amino-1-oxo 1,3-dihydro-2*H*-isoindol-2-yl) piperidine-2,6-dione

The empirical formula for lenalidomide is C₁₃H₁₃N₃O₃, and the gram molecular weight is 259.3.

Lenalidomide is an off-white to pale-yellow solid powder. It is soluble in organic solvent/water mixtures, and buffered aqueous solvents. Lenalidomide is more soluble in organic solvents and low pH solutions. Solubility was significantly lower in less acidic buffers, ranging from about 0.4 to 0.5 mg/ml. Lenalidomide has an asymmetric carbon atom and can exist as the optically active forms S(-) and R(+), and is produced as a racemic mixture with a net optical rotation of zero.

2.1.5 Clinical Pharmacology

2.1.5.1 Mechanism of Action:

The mechanism of action of lenalidomide remains to be fully characterized. Lenalidomide possesses immunomodulatory and antiangiogenic properties. Lenalidomide inhibited the secretion of pro-inflammatory cytokines and increased the secretion of anti-inflammatory cytokines from peripheral blood mononuclear cells. Lenalidomide inhibited cell proliferation with varying effectiveness (IC₅₀s) in some but not all cell lines. Of cell lines tested, lenalidomide was effective in inhibiting growth of Namalwa cells (a human B cell lymphoma cell line with a deletion of one chromosome 5) but was much less effective in inhibiting growth of KG-1 cells (human myeloblastic cell line, also with a deletion of one chromosome 5) and other cell lines without chromosome 5 deletions. Lenalidomide inhibited the expression of cyclooxygenase-2 (COX-2) but not COX-1 in vitro.

2.1.6 Pharmacokinetics and Drug Metabolism

2.1.6.1 Absorption:

Lenalidomide, in healthy volunteers, is rapidly absorbed following oral administration with maximum plasma concentrations occurring between 0.625 and 1.5 hours post-dose. Co-administration with food does not alter the extent of absorption (AUC) but does reduce the maximal plasma concentration (C_{max}) by 36%. The pharmacokinetic disposition of lenalidomide is linear. C_{max} and AUC increase proportionately with increases in dose. Multiple dosing at the recommended dose-regimen does not result in drug accumulation.

Pharmacokinetic analyses were performed on 15 multiple myeloma patients treated in the phase I studies. Absorption was found to be rapid on both Day 1 and Day 28 with time to maximum blood levels ranging from 0.7 to 2.0 hours at all dose levels (5mg, 10mg, 25mg, and 50mg). No plasma accumulation was observed with multiple daily dosing. Plasma lenalidomide declined in a monophasic manner with elimination half-life ranging from 2.8 to 6.1 hours on both Day 1 and 28 at all 4 doses. Peak and overall plasma concentrations were dose proportional over the dosing range of 5mg to 50mg.³³ Exposure (AUC) in multiple myeloma patients is 57% higher than in healthy male volunteers.

2.1.7 Pharmacokinetic Parameters

2.1.7.1 Distribution

In vitro (¹⁴C)-lenalidomide binding to plasma proteins is approximately 30%.

2.1.8 Metabolism and Excretion

The metabolic profile of lenalidomide in humans has not been studied. In healthy volunteers, approximately two-thirds of lenalidomide is eliminated unchanged through urinary excretion. The process exceeds the glomerular filtration rate and therefore is partially or entirely active. Half-life of elimination is approximately 3 hours.

2.1.9 Supplier(s)

Celgene Corporation will supply lenalidomide (Revlimid[®]) to study participants at no charge through Celgene's Revlimid Risk Evaluation and Mitigation Strategy[™] (REMS) (formerly known as RevAssist[®] Program).

2.1.10 Dosage form

Lenalidomide will be supplied as capsules for oral administration.

2.1.11 Packaging

Lenalidomide will be shipped directly to the clinical site. Bottles will contain a sufficient number of capsules for one cycle of dosing.

2.1.12 Labeling

Lenalidomide supplies are dispensed in individual bottles of capsules. Each bottle will identify the contents as study medication. In addition, the label will bear Celgene's name, quantity contained and the standard caution statement as follows: "Caution: New drug - Limited by Federal law to investigational use." Lenalidomide should not be handled by FCBP unless wearing gloves.

The study drug label must be clearly visible. Additional labels must not cover the Celgene label.

2.1.13 Special Handling Instructions

Females of childbearing potential should not handle or administer lenalidomide unless they are wearing gloves.

2.1.14 Prescribing Information

Lenalidomide (Revlimid[®]) will be provided to research subjects for the duration of their participation in this trial at no charge to them or their insurance providers. Lenalidomide will be provided in accordance with the Celgene Corporation's Revlimid REMS[®] program. Per standard Revlimid REMS[®] program requirements, all physicians who prescribe lenalidomide for research subjects enrolled into this trial, and all research subjects enrolled into this trial, must be registered in, and must comply with, all requirements of the Revlimid REMS[®] program.

Drug will be shipped on a per patient basis by the contract pharmacy to the clinic site for IND studies. Only enough lenalidomide for one cycle of therapy will be supplied to the patient each cycle.

2.1.15 Pregnancy Testing

Females must follow pregnancy testing requirements as outlined in the Revlimid REMS[®] program material.

3. OBJECTIVES

3.1 Primary

To determine safety and the maximum tolerated dose of lenalidomide after allo-HCT in AML and MDS subjects with MRD detected by the CD34+ mixed chimerism analysis.

3.2 Secondary

To monitor changes in the CD34+ mixed chimerism after allo-HCT in AML and MDS subjects with detectable MRD in response to escalating doses of lenalidomide.

4. STUDY DESIGN

4.1 Overall Study Design

This is an open-label, phase I study of lenalidomide in after allo-HCT in AML and MDS subjects with MRD detected by the CD34+ mixed chimerism analysis. The study is designed to evaluate the safety profile, maximum tolerated dose and biologic activity of lenalidomide in patients with AML and MDS after allo-HCT. Subjects will be recruited in cohorts of 3. Each subject will receive lenalidomide daily for 21 days per cycle for 2 cycles (42 days). Duration of each cycle is 28 days. The starting dose will be 2.5 mg given orally every other day. Subjects will be evaluated for DLTs from the first dose and until 14 days after the last dose of lenalidomide.

4.2 Dose Escalation

The dose levels of lenalidomide will be as follows:

- Dose Level 1: 2.5 mg PO QOD Day 1-21 for 28-day cycle X 2 cycles
- Dose Level 2: 2.5 mg PO QD Day 1-21 for 28-day cycle X 2 cycles
- Dose Level 3: 5 mg PO QD Day 1-21 for 28-day cycle X 2 cycles
- Dose Level 4: 7.5 mg PO QD Day 1-21 for 28-day cycle X 2 cycles

The dose escalation phase of the study will utilize a standard “3 + 3” design to estimate the MTD for lenalidomide. A description of the statistical characteristics (probabilities of halting or continuing dose escalation) of this design is provided in Appendix G: Statistical Characteristics of the “3+3” Design. For this study, MTD will be defined as the highest dose at which no more than 34% of the subjects observed at a given dose level experience a DLT. Subjects will be individually assessed for safety and DLTs for the purpose of determining the MTD. Three eligible subjects will be enrolled in sequential cohorts at increasing dose levels until at least one (1) DLT is seen between the first dose and 14 days after the last dose of lenalidomide. The following dose escalation rules will be used and applied:

1. Three subjects are initially studied at each dose level.
2. If none of these 3 subjects experience DLT, then the dose is escalated to the next dose level in 3 subsequent subjects.
3. If 1 of these 3 subjects experiences DLT at the current dose, then up to 3 more subjects are recruited at the same dose level.
 - a) If none of these 3 additional subjects experience DLT, then the dose is escalated to the next dose level in 3 subsequent subjects.
 - b) If 1 or more of these 3 additional subjects experiences DLT, then the MTD is considered to have been exceeded and the previous dose level will be the MTD.
4. If 2 or more of the initial 3 subjects at a dose level experience DLT, then the MTD is considered to have been exceeded and dose escalation will be stopped. Up to 3 more subjects are treated at the next lower dose.

A subject must meet one of the following 3 criteria to be evaluable for dose-escalation decisions:

[figure not shown]
1. Completed at least 21 days of lenalidomide without a DLT by 14 days after the last dose of lenalidomide;

2. Experienced a DLT between the first dose and 14 days after the last dose of lenalidomide; or
3. Withdrawn from the study after at least 14 days of lenalidomide administration.

The study ends when there is a maximum dose where 2 or more subjects out of 6 have a DLT, or when the maximum sample size of twenty-four (24) subjects has been reached.

Figure 4 provides an example of how the MTD will be determined in Cycle 1.

Figure 4. Dose Limiting Toxicity Flow Diagram

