
Study Design:
	
This is an open-label, phase I dose escalation study of lenalidomide after allo-HCT in AML and MDS subjects with MRD detected by the CD34+ mixed chimerism analysis. The study is designed to evaluate the safety profile, MTD and biologic activity of lenalidomide after allo-HCT in patients with AML and MDS
 
The dose levels of lenalidomide will be as follows:
 
Dose Level 1: 2.5 mg PO QOD Day 1-21 for 28 day cycle X 2 cycles Dose Level 2: 2.5 mg PO QD Day 1-21 for 28 day cycle X 2 cycles Dose Level 3: 5 mg PO QD Day 1-21 for 28 day cycle X 2 cycles Dose Level 4: 7.5 mg PO QD Day 1-21 for 28 day cycle X 2 cycles
 
Subjects will be enrolled in cohorts of three (3). Lenalidomide will be administered for 21 consecutive days in a 28 day cycle X 2 cycles. The starting dose will be 2.5 mg given orally every other day for 21 days.

Subjects will be individually assessed for safety and dose limiting toxicity (DLT) for the purpose of determining the MTD .Three eligible subjects will be enrolled in sequential cohorts at increasing dose levels until at least one DLT is seen between the first dose and 14 days after the last dose of lenalidomide. For this study, MTD will be defined as the highest dose which no more than 34% of the subjects observed at a given dose level experience a DLT. The following dose escalation rules will be used and applied:

1. Three subjects are initially studied at each dose level.
2. If none of these 3 subjects experience DLT, then the dose is escalated to the next dose level in 3 subsequent subjects.
3. If 1 of these 3 subjects experiences DLT at current dose, then up to 3 more subjects are accrued at the same level.
 - a) If none of these 3 additional subjects experience DLT, then the dose is escalated to the next dose level in 3 subsequent subjects.
 - b) If 1 or more of these 3 additional subjects experiences DLT, then the MTD is considered to have been exceeded and the previous dose level will be the MTD.
4. If 2 or more of the initial 3 subjects at a dose level experience DLT, then the MTD is considered to have been exceeded and dose escalation will be stopped. Up to 3 more subjects are treated at the next lower dose.

A subject must meet one of the following 3 criteria to be evaluable for subsequent dose-escalation decisions:

1. Complete at least 21 days of lenalidomide without a DLT by 14 days after the last dose of lenalidomide;

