2. Experienced a DLT between the first dose and 14 days after the last dose of lenalidomide; or
3. Withdrawn from the study after at least 14 days of lenalidomide administration.

If a subject does not meet any of these criteria, the subject is not evaluable for dose escalation decisions and will be replaced in that cohort. No more than 3 subjects will be added simultaneously to a dose cohort during dose escalation.

The study ends when there is a maximum dose where 2 or more subjects out of 6 have a DLT, or when the maximum sample size of twenty four (24) subjects has been reached.

Dose Limiting Toxicity

DLT will be defined as any of the following adverse events that are not clearly unrelated to drug administration or treatment-emergent from lenalidomide and constitute a change from baseline irrespective of outcome. For the purpose of dose-escalation decisions and MTD

	
determination, only DLTs that occur within 14 days after the last dose of lenalidomide administration will be taken into account.
 
 1. Grade 3 or greater nausea, diarrhea, or vomiting despite the use of maximal medical intervention; 2. Grade 3 or greater acute GVHD despite the use of maximal medical intervention; 3. Any other clinically significant non-hematologic toxicity of grade 3 or greater considered not related to the underlying disease or intercurrent illness; 4. Grade 3 or greater neutropenia; 5. Grade 4 thrombocytopenia or platelet count ≤ 50 thou/mm³ by day 28 of lenalidomide administration; or 6. Any treatment-related effect leading to a subject missing 3 or more doses of lenalidomide. 
Correlative Studies:
 
Peripheral blood will be collected to examine the CD34+ specific chimerism.

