6.1 Treatments to be Administered

Lenalidomide will be administered for a total of 42 days. The starting dose will be 2.5 mg given orally every other day on days 1-21 of a 28-day cycle for 2 cycles. Dose escalations and de-escalations will be made until the MTD is reached.

To ensure subject safety in the dose-escalation portion of the study, an early stopping rule will be implemented in the event that a DLT rate of greater than 34% is observed at a dose level of 2.5 mg, the lowest dose level to be evaluated in this study. In the event a DLT rate of greater than 34% observed at the starting dose of 2.5 mg orally every other day, the study will be terminated.

The dose levels of lenalidomide will be as follows:

- Dose Level 1: 2.5 mg PO QOD Day 1-21 for 28-day cycle X 2 cycles
- Dose Level 2: 2.5 mg PO QD Day 1-21 for 28-day cycle X 2 cycles

- Dose Level 3: 5 mg PO QD Day 1-21 for 28-day cycle X 2 cycles
- Dose Level 4: 7.5 mg PO QD Day 1-21 for 28-day cycle X 2 cycles

Doses should be taken at approximately the same time each day.

Subjects must be instructed to swallow lenalidomide capsules whole with water at the same time each day. Do not break, chew or open the capsules.

If a dose of lenalidomide is missed, it should be taken as soon as possible on the same day. If it is missed for the entire day, it should not be made up.

Subjects who take more than the prescribed dose of lenalidomide should be instructed to seek emergency medical care if needed and contact study staff immediately.

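### At 2 DLTs in 6 subjects (33.3%) the 34% definition accepts the dose as the MTD, while rule 3b names the level below

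*Combined protocol and SAP*

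**What the plan says.** The primary objective (3.1) is "To determine safety and the maximum tolerated dose of lenalidomide after allo-HCT". Two kinds of text then decide which dose that is.

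- **Percentage texts.** Section 4.2 defines the MTD as the "highest dose at which no more than 34% of the subjects observed at a given dose level experience a DLT"; the Synopsis has the same definition ("highest dose which no more than 34% of the subjects observed at a given dose level experience a DLT"). Section 6.1 says that in the event of "a DLT rate of greater than 34% observed at the starting dose of 2.5 mg orally every other day, the study will be terminated". Section 11.3 sets a stopping rule for any dose cohort above 34%.
- **Count texts.** In the Synopsis and 4.2, after 1 DLT in the first 3, "then up to 3 more subjects are recruited at the same dose level" (4.2 wording). If any added subject has a DLT, rule 3b says "then the MTD is considered to have been exceeded and the previous dose level will be the MTD". Under rule 4, 2 or more DLTs in the first 3 stop escalation and "Up to 3 more subjects are treated at the next lower dose". The Synopsis and 4.2 add: "The study ends when there is a maximum dose where 2 or more subjects out of 6 have a DLT". Section 11.3 repeats that 2-of-6 rule directly after its 34% trigger. Appendix G computes its stopping probabilities with 2 or more DLTs as the stopping event.

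No text available for this review says which kind governs if they differ.

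**The concern.** Two of six is 33.3%. That is within a 34% ceiling, yet rule 3b says the MTD has been exceeded. One observed result therefore yields two different MTDs, one level apart.

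The MTD is part of the primary objective, and the Synopsis presents this study as the basis for a phase II trial. Adjacent levels differ materially in dose per cycle: 11 × 2.5 = 27.5 mg at Level 1 (alternate days, days 1 to 21), then 21 × 2.5 = 52.5, 21 × 5 = 105 and 21 × 7.5 = 157.5 mg. The two candidate labels differ 1.9-, 2.0- and 1.5-fold when 2/6 occurs at Levels 2, 3 and 4.

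Two gaps sit beside this. At Dose Level 1 rule 3b has no previous level to name, and the 6.1 trigger does not fire at 2/6. Rule 3b is also worded for expansion after 1/3, so it does not reach a lower level that arrives at 2/6 through the rule 4 expansion (0/3, then 2/3). The definition would accept that level.

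**Working it through.** **1. Reproduce Appendix G.** Let p be the true DLT rate, b0 = (1−p)³ and b1 = 3p(1−p)². Escalation needs 0/3, or 1/3 then 0/3, so P(stop) = 1 − b0 − b1·b0. At p = 0.33, b0 = 0.3008 and b1 = 0.4444. P(escalate) = 0.3008 + 0.4444 × 0.3008 = 0.4344 and P(stop) = 0.5656; the plan prints 0.43 and 0.57. All ten printed escalation values reproduce to rounding. Had 2/6 counted as acceptable, the 0.43 would be 0.4344 + 0.4444² = 0.63. Appendix G is therefore built on rule 3b's cut-off.

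**2. Compare the texts on every final result, full cohorts on the way up.**

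| Result | Rate | 34% definition | Rules 2 to 4 |
|---|---|---|---|
| 0/3 | 0% | accepts | escalate |
| 1/6 | 16.7% | accepts | escalate |
| **2/6** | **33.3%** | **accepts** | **exceeded** |
| 3/6 | 50% | rejects | exceeded |
| 4/6 | 66.7% | rejects | exceeded |
| 2/3 | 66.7% | rejects | exceeded |
| 3/3 | 100% | rejects | exceeded |

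1/3 is interim. If an expansion is cut short, 2/4 (50%) and 2/5 (40%) are above 34%, so the texts agree. A rule 4 expansion of a level at 0/3 can end at 0/6, 1/6, 2/6 or 3/6; again only 2/6 is contested.

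**3. Single-level frequency.** P(1/3 then 1/3) = b1².

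| p | b1 | b1² |
|---|---|---|
| 0.10 | 0.243 | 5.9% |
| 0.20 | 0.384 | 14.7% |
| 0.33 | 0.444 | 19.8% |
| 0.40 | 0.432 | 18.7% |

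**4. Trial-wide effect.** The documents give no dose-toxicity curve, so four are assumed. Further assumptions: rule 4 adds 3 subjects when the lower level has only 3; a level cleared at 1/6 is not expanded again; nothing is added after rule 3b. The outcome is the chance that the named MTD has a true DLT rate of 0.33 or more.

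| Curve (Levels 1–4) | 2/6 after 1/3, Levels 2–4 | Rule 3b followed | Definition followed throughout |
|---|---|---|---|
| A: 0.05 at all | 5.2% | 0% | 0% |
| B: 0.05, 0.10, 0.20, 0.33 | 31.1% | 27.2% | 39.5% |
| C: 0.10, 0.20, 0.33, 0.50 | 30.0% | 25.4% | 40.2% |
| D: 0.20, 0.30, 0.40, 0.50 | 21.8% | 9.5% | 17.1% |

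Curve C in full:
- P(reach Level 3) = 0.9061 × 0.7086 = 0.6421.
- With rule 3b, Level 3 is named with probability 0.2064 and Level 4 with 0.6421 × 0.4344 × 0.1719 = 0.0479; total 0.2543.
- The definition adds 2/6 at Level 3 after 1/3: 0.6421 × 0.1975 = 0.1268.
- It also adds a Level 3 expansion ending at 2/6, that is 0/3 at Level 3, at least 2/3 at Level 4, then 2/3 at Level 3: 0.6421 × 0.3008 × 0.5 × 0.2189 = 0.0211.
- Total 0.2543 + 0.1268 + 0.0211 = 0.402.

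Curve D likewise: 0.0950 + 0.0654 + 0.0109 = 0.171. Curve B gains only from 2/6 at Level 4: 0.2715 + 0.1234 = 0.395. In C and D a 2/6 at Level 4 moves the label between two levels already at 0.33 or more, so it adds nothing.

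**5. Dose Level 1.** 2/6 after 1/3, where no previous level exists, has probability b1² = 1.8%, 1.8%, 5.9% and 14.7% under A to D.

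**The case against.** The operative text is clear. After the general 34% sentence, 4.2 sets out the escalation rules to be applied, and rule 3b deals expressly with 2/6 after 1/3. The study-end rule and Appendix G agree with it, and the design is described as a standard 3 + 3. A reader who let the percentage win would be overriding a specific instruction in the same section. The study is also declared descriptive. Figure 4, which could not be seen for this review, is introduced as an example of MTD determination and may show how 2/6 is handled. At Dose Level 1 the 2-of-6 rule still ends the study.

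Most of this stands. Rule 3b is the more likely reading, and it gives the lower dose. What does not fall away is that the formal definition of a primary-objective quantity contradicts its own algorithm, that 11.3 holds both cut-offs, and that rule 3b does not cover a rule 4 expansion ending at 2/6. An example figure would not remove the conflicting sentence.

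Three stronger inferences are tempting and unsupported:
- *Patients would be escalated past a toxic dose.* At 2/6 escalation stops under either text.
- *Up to 31% of trials would name the wrong MTD.* Those percentages count how often the texts conflict under assumed curves; if rule 3b is followed, no label changes.
- *Appendix G is wrong.* It reproduces under the count rule and needs no change.

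**Conclusion.** The inconsistency is real and confined to 2/6. The 34% figure is the outlier against rule 3b, the study-end rule and Appendix G. Only the declared MTD label is affected, by one level.

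The single-level frequencies (5.9% to 19.8% at the true rates shown) rest only on independent subjects with a common DLT rate. The trial-wide increases (none for A, 12.3 percentage points for B, 14.8 for C, 7.6 for D) also need the assumed curves and require the less likely reading to be followed throughout, including for rule 4 expansions. They bound what the ambiguity could do rather than predict it. The wording should be corrected because it sets the decision threshold for the primary objective; it is not a participant-safety finding.

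**What to change.** - **Synopsis and 4.2:** replace the 34% definition with *the highest dose level with fewer than 2 DLTs (0 of 3, or at most 1 of 6) once any expansion under rule 3 or rule 4 is complete*. A level at 1/3 then stays undecided until rule 3 is finished, and a rule 4 expansion ending at 2/6 is clearly not the MTD.
- **6.1 and 11.3:** replace the 34% triggers with *2 or more DLTs among up to 6 evaluable subjects at a dose level*. In 11.3, add that the rule 4 expansion of the level below still proceeds.
- **Dose Level 1:** state that 2 or more DLTs there end the study with no MTD established.

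Appendix G is unchanged. The cost is wording in four places, with no extra subjects or procedures. Lowering the ceiling to below 33.3% would also settle 2/6 after 1/3, but the count wording matches the rules directly and avoids a percentage that falls next to an attainable result.

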11.3 Study Stopping Rules

To reduce the risk of exposing subjects to an excessively toxic dose level, a stopping rule will be implemented if more than 34% of subjects in a given lenalidomide dose cohort experience a DLT. The study ends when there is a dose where 2 or more subjects out of 6 have a DLT, or when the maximum sample size of twenty-four (24) subjects has been reached.

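### Rules 3b and 4 both conclude that the MTD has been exceeded, but only Rule 4 adds subjects at the lower dose, so the declared MTD can rest on 0 DLTs in 3 subjects

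*Combined protocol and SAP*

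**What the plan says.** The rules stand in Section 4.2 and, in the same form, in the synopsis.

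- Start: "Three subjects are initially studied at each dose level".
- Rule 2 (0/3): "If none of these 3 subjects experience DLT, then the dose is escalated to the next dose level in 3 subsequent subjects". The level is left with 3 subjects.
- Rule 3 (1/3): "then up to 3 more subjects are recruited at the same dose level".
- Rule 3a (1/3, then 0/3): "If none of these 3 additional subjects experience DLT, then the dose is escalated to the next dose level". The level is left with 6 subjects.
- Rule 3b (1/3, then at least 1 in 3): "then the MTD is considered to have been exceeded and the previous dose level will be the MTD".
- Rule 4 (at least 2 in the first 3): escalation stops and "Up to 3 more subjects are treated at the next lower dose".

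Section 4.2 defines the MTD as the highest dose with an observed DLT proportion of at most 34% and sets no minimum number of subjects. Section 13.1 plans 3 to 6 subjects per level and a total of 24.

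On stopping, Section 11.3 says "a stopping rule will be implemented if more than 34% of subjects in a given lenalidomide dose cohort experience a DLT" and then "The study ends when there is a dose where 2 or more subjects out of 6 have a DLT". Section 4.2 and the synopsis carry nearly the same study-end sentence. Section 6.1 terminates the study if the DLT rate at the starting dose exceeds 34%. Appendix G gives escalation probabilities for a single level only.

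**The concern.** Suppose a level was passed on 0/3 and the level above then proves too toxic. If the upper level fails within its first 3 subjects, Rule 4 allows more subjects at the lower level. If it fails only after 6, Rule 3b names the lower level the MTD at once, and the study-end sentence leaves no room for anything further. The data at the lower level are identical in both cases. The timing of DLTs one level up decides how much evidence supports the MTD, and no section gives a reason for the difference.

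The MTD is the primary objective, and the synopsis calls this study the foundation for a phase II trial. Zero DLTs in 3 subjects is weak support for a dose that is to be carried forward.

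The same rules disagree with the MTD definition. Two DLTs in 6 is 33.3%, which satisfies the 34% limit, yet Rule 3b treats it as exceeding the MTD. At Level 1, exactly 2/6 falls outside the termination rule in Section 6.1, and Rule 3b points to a previous level that does not exist.

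**Working it through.** **Single-level formulas, with p the true DLT probability**

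- Pass on 0/3: (1−p)³
- Pass on 1/6 (Rule 3a): 3p(1−p)² × (1−p)³
- Stop by Rule 3b: 3p(1−p)² × [1−(1−p)³]
- Stop by Rule 4: the remainder

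**Check against Appendix G.** The two pass probabilities sum to 0.973, 0.906, 0.709, 0.434, 0.309, 0.172, 0.082, 0.044, 0.032 and 0.009 for p = 0.05, 0.1, 0.2, 0.33, 0.4, 0.5, 0.6, 0.67, 0.7 and 0.8. These agree with the printed row (0.97, 0.91, 0.71, 0.43, 0.31, 0.17, 0.08, 0.04, 0.03, 0.01), so the rules have been read as the plan reads them.

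**Share of all trials with a Rule 3b MTD on 3 subjects.** This is the sum over Levels 2 to 4 of P(reach the level) × P(Rule 3b stop there) × P(the level below was passed on 0/3, given that it was passed). The documents attach no DLT rate to any dose, so every curve is an assumption. For 5/10/20/33%:

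| Level | P(reach) | P(Rule 3b) | Level below passed on 0/3 | Product |
|---|---|---|---|---|
| 2 | 0.9734 | 0.0659 | 0.8808 | 0.0565 |
| 3 | 0.8821 | 0.1874 | 0.8045 | 0.1330 |
| 4 | 0.6251 | 0.3107 | 0.7225 | 0.1403 |

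The sum is 0.330. As an example of the entries at Level 3: 3 × 0.2 × 0.8² × (1−0.8³) = 0.384 × 0.488 = 0.1874, and 0.729/0.9061 = 0.8045. A further 9.4% of trials stop by Rule 3b above a level that already has 6 subjects; these are not counted.

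**Other assumed curves**

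| DLT rates, Levels 1-4 (%) | Rule 3b MTD on 3 subjects |
|---|---|
| 5/10/20/40 | 34.2% |
| 10/20/33/50 | 34.4% |
| 10/20/30/40 | 34.6% |
| 20/33/40/50 | 25.3% |
| 5/33/40/50 | 39.6% |
| 5/5/10/20 | 20.1% |
| 33/33/33/33 | 15.2% |
| 33/40/50/60 | 13.7% |
| 10/10/10/10 | 13.1% |
| 5/5/5/5 | 4.8% |

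The 15 strictly rising curves that can be built from the Appendix G rates 0.05 to 0.5 give 25.3% to 39.6%, median 34.7%. The 126 non-decreasing curves from the same rates give 4.8% to 40.0%, median 31.4%.

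**Precision at the declared level.** Exact two-sided 95% upper limits are 71% for 0/3 (1−0.025^(1/3) = 0.708), 46% for 0/6 (1−0.025^(1/6) = 0.459) and 64% for 1/6 (Clopper-Pearson, 0.641).

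**What 3 further subjects could show.** After 0/3, the chance of 2 or more DLTs in the next 3 is 3p²(1−p) + p³: 2.8% at p = 0.10, 10.4% at 0.20, 25.5% at 0.33 and 35.2% at 0.40.

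**Consistency with 34%.** 2/6 = 33.3% is below the limit; 2/3 = 66.7% and 3/6 = 50% are above it.

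**The case against.** **Rule 4 is not a firm standard of 6.** A reader might infer that Rule 4 secures 6 subjects at the MTD and that only Rule 3b falls short. The text does not support that. Rule 4 says up to 3 more, sets no minimum and gives no decision rule for them. This stands: Rule 4 needs completing as well.

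**Section 11.3 need not cut off Rule 4.** Since 2/3 exceeds 34%, one could infer that the stopping rule blocks Rule 4's own expansion. That is only one possible reading. The sentence is aimed at an excessively toxic dose level, and the study-end condition is a separate sentence about 2 of 6. Read together, 2/3 may stop that level and leave Rule 4 to proceed.

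**Level 1 is largely covered.** It is tempting to say that the plan has no rule for failure at Level 1. Section 6.1 terminates above 34%, which covers 2/3 and 3/6 or more. At exactly 2/6 the study-end sentence applies. The gap is the conclusion to be drawn about the MTD in that one case.

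**The size depends on the curve.** This is correct, and a third should not be quoted without its scenario and range.

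**The gain can be modest.** Completion may end at 1/6, whose upper limit of 64% is not far below 71%. At a true rate of 20%, the 3 added subjects show exactly one DLT in 38% of cases (3 × 0.2 × 0.8² = 0.384). The study is descriptive, and Section 13.1 allows levels of 3. So 3 subjects at the MTD is not in itself an error. The unexplained difference between the two routes remains.

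**Figure 4 is not visible** in the text available for review. It illustrates how the MTD is determined and might show a further step.

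**Conclusion.** The point holds as an inconsistency in the rules that determine the primary result. Rules 3b and 4 draw the same conclusion and treat the lower dose differently, and the study-end sentences close the trial at the Rule 3b trigger. Rule 3b also contradicts the 34% definition at 2/6, and no MTD conclusion is stated for 2/6 at Level 1.

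Under assumed DLT rates, about 25-40% of trials on strictly rising curves (Appendix G rates 0.05 to 0.5) would declare a Rule 3b MTD on 0/3, with 33% for 5/10/20/33%. Flat, shallow or very toxic curves give roughly 5-20%. The calculation assumes independent subjects, full cohorts and the rules followed literally. It leaves out 0/3 at Level 4, for which the rules state no outcome.

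The documents do not support the stronger inferences that an MTD declared on 3 subjects is wrong, or that the plan lacks any protection at Level 1.

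**What to change.** Reconcile Rules 3b and 4, the 34% MTD definition and the study-end and termination sentences in the synopsis and Sections 4.2, 6.1 and 11.3, so that both routes handle a 3-subject lower level in the same way. One option is to complete that level to 6 evaluable subjects, within the 3 to 6 planned in Section 13.1, before the MTD is declared. The revised text should also:

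- state how the added subjects are judged, under Rule 4 as well;
- settle whether 2/6 meets or exceeds the MTD, and what is concluded for 2/6 at Level 1;
- word the study-end sentence so that it stops escalation and not the confirmation;
- bring Figure 4 into line.

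Under that option each expanded level costs up to 3 more subjects and one more DLT window. A window is about 63 days from first dose on the stated schedule (28 + 21 + 14). The average is about 1 subject per trial (3 × 0.33) before any further step-down. The worst case is a Rule 3b stop at Level 4 with 0/3 at each lower level and step-down through all three: 9 subjects over three windows. The total is then 6 + 3 × 3 + 9 = 24, which is the cap. It holds for evaluable subjects only, so the plan should state how replacements count: Section 5.1 counts those who receive lenalidomide, Section 13.1 those evaluated.
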